9. RESEARCH METHODS

9.1 STUDY DESIGN

Study design:

- Descriptive cohort study

Comparison group

- OAD group, DPP-4 inhibitors group, SU group, BG group, TZD group, α -GI group, and Glinide group.

Strength of the study design

- Up-to-date information can be obtained and nationwide actual treatment status can be illustrated with using large-scale real-world database.

Analysis

- First analysis: type and dosage of drug prescribed for T2DM patients.
- [REDACTED]
- Main measures: number of patients, baseline characteristics at index month (age, sex), prior and concomitant use of glucose-lowering medications and insulin (type, dose), comorbidities (types and their percentages of patients), stage of RI defined by eGFR or serum creatinine value, glucose-lowering medications and their dosages (based on daily dose) for patients with RI, [REDACTED]
- [REDACTED]

Potential limitation

- The data held in MDV database is collected from DPC hospitals, not GP data. However they are including outpatient data because many of Japanese patients prefer to visit a hospital even though chronic disease.
- The rate of laboratory test data held in MDV database is limited. About 350,000 patients out of 2,600,000 patients (13.5%, April 2008 ~ April 2016) have laboratory data.
- The MDV database does not hold the time diagnosis of T2DM if it is out of study period. Therefore the onset date of diabetes or the first record of T2DM cannot obtain for all patients.
- The information on medication is based on prescribed record, not include adherence result. It means that exact dosage may not reveal actual dispensed prescription and dosage perfectly.
- Laboratory test date is not exactly matched with the index day of the first prescription of OAD. The sample size will have some impacts (reduction) to assure simultaneous timing of data. The latest lab result 30 days before the index date will be considered the status at the time of prescription
- All information of each patient is from consent given DPC hospitals. If patients have visits to other medical institutions, these data are not included in the MDV data.

- MDV database is composed of data from patients who hospitalized in DPC hospital so that more severe patient will be included in the database.

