9.2 SETTING

Medical Data Vision (MDV) clinical database is used.

Inclusion criteria

[figure not shown]
- Patients with T2DM (ICD code: E11 or E14).
- Patients must have their first prescription (defined as index date*) for any study drugs between 01/01/2014 and 30/09/2016.
- Patients must have at least 6 months enrolment verified by the presence of any record except for the study drug prescriptions within the database (look back period) prior to the index date for each drug.

Exclusion criteria

- Patients who were under 40 y.o. at the time of diagnosis of diabetes.
- Patients with record of type 1 diabetes mellitus (ICD code: E10).
- Patients who prescribed the study drugs during 6 month prior to index date for each drug.
- Patients whose mean visit interval are more than 92 days

*Index date is defined as follows:

- In case of comparing drugs within class, index date is defined as the date of first prescription for any study drugs as general name. Change of dosage is not counted as the index.
- In case of comparing drugs between class, index date is defined as the date of first prescription for study drug of class. Change of dosage is not counted as the index.

* The hospitalization period is not included in the mean visit interval.

Figure 1 Definition of Index data(date of first prescription for any study drugs)

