9.4 DATA SOURCES

Medical Data Vision (MDV) clinical database. The database is health insurance claim database. As of end of July 2015, facilities: 200, patients: 10.95 million, which is covering approximately 12% of acute hospitals in Japan. Lab results are also available but number of hospitals providing with lab test results are limited.

Study period is from 01/01/2014 to 30/09/2016 in MDV database at the time of study protocol approval.

The MDV database is broadly representative of the Japanese population with similar distribution comparing with Japanese population; therefore we believe our study sample will provide reasonable description of the characteristics of patients treated with diagnosis of type 2 diabetes mellitus in the general Japanese population. There is research experience using the data, 19 publications, 5 conference presentations (as of August 2015).

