9.5 STUDY SIZE

All available data from 01/01/2014 to 30/09/2016 will be included to ensure the maximum number of patient.

All patients with a prescription of OADs and DPP-4 inhibitors from 01/01/2014 to 31/08/2015 and a diagnosis of T2DM is estimated that approximately 9,890 and 7,579 patients respectively have been prescribed a study drug in the MDV database to be included in the study.

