9.7 DATA ANALYSIS

9.7.1 Main analysis

- For the primary objective, descriptive statistics of patients prescribed each compound and each class of OAD at least once will be presented for the baseline demographic and clinical characteristics:
 - Number of patients (n, % of total patients)
 - Age (mean ± SE, mean ± SD)
 - Sex
 - Concomitant medications (drug prescribed at index day) :
 - Use of biguanide (Yes/No)
 - Use of sulfonylurea (Yes/No)
 - Use of thiazolidinediones (Yes/No)

- Use of glinide (Yes/No)
- Use of α -GI (Yes/No)
- Use of GLP-1RA (Yes/No)
- Use of SGLT2 inhibitors (Yes/No)
- Use of insulin (Yes/No)
- Premedications (drug prescribed before index day):
 - Use of biguanide (Yes/No)
 - Use of sulfonylurea (Yes/No)
 - Use of thiazolidinediones (Yes/No)
 - Use of glinide (Yes/No)
 - Use of α -GI (Yes/No)
 - Use of GLP-1RA (Yes/No)
 - Use of SGLT2 inhibitors (Yes/No)
 - Use of insulin (Yes/No)
- Comorbidities:
 - Hypertension: Percentage of patients with a diagnosis of hypertension
 - Ischemic heart disease (IHD): Percentage of patients with a diagnosis of IHD
 - Myocardial Infarction (MI): Percentage of patients with a diagnosis of MI
 - Heart Failure (HF): Percentage of patients with a diagnosis of HF
 - Stroke: Percentage of patients with a diagnosis of stroke
 - Renal impairment: Percentage of patients with a diagnosis of renal impairment
 - Amputation: Percentage of patients with a diagnosis of amputation

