9.9 LIMITATIONS OF THE RESEARCH METHODS

- The data held in MDV database is collected from DPC hospitals, not GP data. However they are including outpatient data because many of Japanese patients prefer to visit a hospital even though chronic disease.
- The rate of laboratory test data held in MDV database is limited. About 350,000 patients out of 2,600,000 patients (13.5%, April 2008 ~ April 2016) have laboratory data.
- The MDV database does not hold the time diagnosis of T2DM if it is out of study period. Therefore the onset date of diabetes or the first record of T2DM cannot obtain for all patients.
- The information on medication is based on prescribed record, not include adherence result. It means that exact dosage may not reveal actual dispensed prescription and dosage perfectly.
- Laboratory test date is not exactly matched with the index day of the first prescription of OAD. The sample size will have some impacts (reduction) to assure simultaneous timing of data. The latest lab result 30 days before the index date will be considered the status at the time of prescription
- All information of each patient is from consent given DPC hospitals. If patients have visits to other medical institutions, these data are not included in the MDV data.
- MDV database is composed of data from patients who hospitalized in DPC hospital so that more severe patient will be included in the database.

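### Does the under-40-at-diagnosis exclusion need a stated diagnosis date and search start before the cohort can be built?

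*Combined protocol and SAP*

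**What the plan says.** The exclusion list in section 9.2, repeated in the abstract, removes "Patients who were under 40 y.o. at the time of diagnosis of diabetes". The inclusion list identifies T2DM by ICD codes E11 or E14 but attaches no date to the code. The variable lists in 9.3 and 9.3.3 give age at the index date and contain no diagnosis date.

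On what the database holds, section 9.1 states: "The MDV database does not hold the time diagnosis of T2DM if it is out of study period". Section 9.9 repeats this and draws the consequence: "Therefore the onset date of diabetes or the first record of T2DM cannot obtain for all patients".

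On the span of data, section 9.4 states: "Study period is from 01/01/2014 to 30/09/2016 in MDV database at the time of study protocol approval". Section 9.5 adds: "All available data from 01/01/2014 to 30/09/2016 will be included to ensure the maximum number of patient". Two other statements reach further back. The entry rule in 9.2 is "Patients must have at least 6 months enrolment verified by the presence of any record except for the study drug prescriptions", counted back from each index date. The laboratory limitation in 9.9 reads: "About 350,000 patients out of 2,600,000 patients (13.5%, April 2008 ~ April 2016) have laboratory data".

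**The concern.** An eligibility rule rests on a date that the protocol itself says is missing for some patients, and no rule is written for those patients. Even on the natural reading, age at the first recorded diabetes code, the analyst must choose where the search begins. The documents mention three possible starts: 01/01/2014, about 01/07/2013, and April 2008. None is assigned to the age rule.

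The choice can matter for an individual. A patient in the forties at index whose only pre-40 code lies before 2014 is kept by a study-period search and dropped by a search of older history. Cohort characteristics are the primary outcome and age is a reported row, so what is at stake is who passes the age screen and how the younger end of the age and comorbidity tables looks. The independent code check in section 9.8 would also have no written specification of this rule to check against.

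**Working it through.** There is no stated figure to reproduce: the rule carries no number beyond 40 years, and the study has no power calculation. The check is date arithmetic on the three starts, followed by a reading of which start the text supports.

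**Reach of each search.** The highest index age at which a pre-40 code can be seen is 40 plus the years searched before the index date (days divided by 365.25).

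| Search start | Where it comes from | Index 01/01/2014 | Index 30/09/2016 |
|---|---|---|---|
| 01/01/2014 | Study period, 9.4 and 9.5 | 40 + 0.00 = 40.0 | 40 + 2.75 = 42.75 |
| about 01/07/2013 | 6-month look-back, 9.2 | 40 + 0.50 = 40.5 | 40 + 3.25 = 43.25 |
| April 2008 | Laboratory-data range, 9.1 and 9.9 | 40 + 5.75 = 45.75 | 40 + 8.50 = 48.5 |

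The printed laboratory range ends in April 2016 and spans about 8 years. The 8.50 in the table joins its start to the end of the study period. Only the start affects eligibility.

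**Can a decision flip?** Take an assumed patient born 01/06/1971, with diabetes codes on 01/03/2010 and 01/05/2014 and index 01/11/2014 (age 43.4). A search from April 2008 finds the first code at 38.75 and excludes the patient. A search from 01/07/2013 or from 01/01/2014 finds the first code at 42.9 and includes the patient. So a flip is possible, but here only April 2008 produces it.

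**Which start does the text support?** April 2008 appears only as the period over which the laboratory-data rate was counted. The limitation that follows it in 9.1 and 9.9 is the one that speaks about diagnosis, and it says diagnosis time is not held outside the study period. Sections 9.4 and 9.5 set the same limits on the study period and the data to be included. To use April 2008, an analyst would have to set those statements aside and borrow a date range given for another purpose.

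**What remains.** The look-back does imply records before 2014 for the earliest index dates, which sits awkwardly with the diagnosis-time limitation. Between the two supported starts the difference is 43.25 − 42.75 = 0.50 year of visible age at the last index date, and 40.5 − 40.0 = 0.50 year at the first.

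**Patients with no observable first diagnosis.** An exclusion acts only on patients shown by the record to meet it. Where the record shows no pre-40 code, the patient stays in. That is the ordinary default in database work and needs no separate rule.

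**The case for a change.** The strongest case for a change is that a disclosed limitation is not an instruction. The limitation text never mentions the exclusion, and the study-period reading makes the rule behave almost as an age-at-index screen: someone diagnosed at 25 and indexed at 50 passes. Stating the date variable, the codes and the search start would cost a couple of sentences.

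The omission is real, and so is the weak reach of the rule. But writing the sentences down does not recover diagnoses made before the record begins; the same patients stay in. The one substantive alternative, searching all history held, is a trade-off: it screens patients with long records more strictly than those with short ones. On the protocol's own statement about diagnosis dates, it may not be possible at all. A uniform study-period search is equally defensible.

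A sensitivity figure can be built, but it does not show harm. With the protocol's 9,890 patients (estimated for 01/01/2014 to 31/08/2015 only) and an assumed SD of age of 10 to 14 years, the SE of mean age is 10/√9,890 = 0.10 to 14/√9,890 = 0.14 years. If the patients who switch are 15 to 25 years younger than the rest (assumed), a one-SE shift needs between 0.1006/25 = 0.40% (40 patients) and 0.1408/15 = 0.94% (93 patients). That is how many would be required; nothing in the documents shows that so many exist. A shift of 0.10 to 0.14 years in mean age is also of no consequence in a descriptive table.

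**Conclusion.** The rule is under-specified, but no change to the plan is needed. Analysts would sensibly take age at the first recorded E11 or E14 code in the extract they hold and keep patients with no visible pre-40 code. The documents favour a search over the study period. The competing start with support in the text, about 01/07/2013, differs by half a year of visible age. The wider spread, up to 45.75 to 48.5 years, depends on treating a laboratory-data range as a diagnosis search window and on assuming that diagnosis codes are usable from 2008.

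The number of patients affected cannot be computed, because the documents give no age distribution and no code dates. The leakage of earlier diagnoses is already disclosed in 9.1 and 9.9 and would survive any wording. These patients still have T2DM, and no hypothesis test depends on them. The conclusion rests on one assumption: that the same extract and the same first-code rule are applied across all drug groups, which is the ordinary way to program such a cohort.

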9.3 VARIABLES

Number of patients, age at index date, sex, prior and concomitant use of glucose-lowering medications and insulin, comorbidities and serum creatinine.

Potential confounding for the type and dosage (based on daily dose) of medications and their age, sex, comorbidities, serum creatinine.

9.3.1 Exposures

Prescriptions for an OAD issued between 01/01/2014 and 30/09/2016 described below:

- DPP-4 inhibitors therapies:
 - Alogliptin
 - Alogliptin/Pioglitazone single-pill combination
 - Anagliptin
 - Linagliptin
 - Saxagliptin
 - Sitagliptin
 - Teneligliptin
 - Vildagliptin
- Sulfonylurea therapies:
 - Acetohexamide
 - Glyclopamide
 - Glibenclamide
 - Chlorpropamide
 - Tolbutamide Tablets
 - Tolbutamide Powders
 - Gliclazide
 - Glimepiride
 - Glimepiride Orally-disintegrating tablet
- Biguanide therapies:
 - Buformine
 - Metformin
- Thiazolidinedione therapies:
 - Pioglitazone
 - Pioglitazone Orally-disintegrating tablet
 - Glimepiride/Pioglitazone single-pill combination OD
 - Metformin/Pioglitazone single-pill combination OD
- α -GI:
 - Acarbose
 - Acarbose Orally-disintegrating tablet
 - Voglibose
 - Voglibose Orally-disintegrating tablet
 - Miglitol
 - Miglitol Orally-disintegrating tablet
- Glinide therapies:
 - Nateglinide

- Mitiglinide
- Repaglinide
- Mitiglinide/Voglibose single-pill combination

* Combined in general name if the drug has been sold in several brand name.

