7. RATIONALE AND BACKGROUND

Renal impairment (RI) is a common complication in patients with T2DM. In Japanese patients with T2DM, about 40% of patients have microalbuminuria or macroalbuminuria [1], and other report shows that 55% of Japanese patients with T2DM suffer from mild to moderate renal dysfunction [2].

Many of OADs are contraindicated in severe RI patients or should be carefully administered in patients with declined renal function. For biguanide, a risk of lactic acidosis increases in RI and biguanide is contraindicated in moderate or severe RI. Pioglitazone is used with no contraindication in patients with RI in USA, meanwhile in Japan it is contraindicated in severe RI patients and it requires careful administration to mild to moderate RI patients. Glinides and α -GIs also require careful administration in RI patients although the levels of severity of RI with caution are different from each drug in some measure.

The prescriptions of DPP-4 inhibitors are rapidly increasing in T2DM patients after its introduction to the Japanese clinical practice [3]. The reason of this trend might result from well-balanced drug characteristics with its safety profile, especially low frequency of hypoglycaemia and its acceptable efficacy on blood glucose lowering. Therefore many of physicians consider DPP-4 inhibitor is widely chosen as a monotherapy and one of combination therapy.

As for DPP-4 inhibitors administered on a daily basis, there are seven single ingredient drugs in this class and their dose-reduction manners are various in RI patients. Linagliptin and teneligliptin are not required dose reduction. On the other hand, other five drugs are recommended dose reduction or careful administration. Furthermore sitagliptin and alogliptin have four and three of drug formulations of different contained amount respectively in Japan. Japanese physicians are required proper use of complicated regimen in accordance with each patient's renal function.

Currently, there is no publication of actual situation on the prescription patterns of OADs and dose-reduction especially in DPP-4 inhibitors and other OADs needed to dose-reduction. However from viewpoint of appropriate use, relevant dose-reduction can contribute patients benefit. This study aims to assess the actual condition of dose selection of OADs among RI patients in Japan by using MDV database.

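### Each single-pill combination is listed under one class only, so class-level counts and index dates leave out its other component; washout and medication flags have no stated rule

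*Combined protocol and SAP*

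**What the plan says.** Section 9.3.1 sorts the study drugs into six classes. Four entries are single-pill combinations, and each appears once:

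- "Alogliptin/Pioglitazone single-pill combination" under DPP-4 inhibitors
- "Glimepiride/Pioglitazone single-pill combination OD" under thiazolidinediones
- "Metformin/Pioglitazone single-pill combination OD" under thiazolidinediones
- "Mitiglinide/Voglibose single-pill combination" under glinides

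The list has one footnote, "Combined in general name if the drug has been sold in several brand name". It merges brands and does not deal with components.

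Section 9.2 ties the class-level index date to the class list: "In case of comparing drugs between class, index date is defined as the date of first prescription for study drug of class". The same section excludes patients who had study drugs prescribed in the six months before the index date for each drug. Section 9.1 names the six classes, and an overall OAD group, as the comparison groups. Section 9.7.1 describes patients by compound and by class, with yes/no rows for concomitant and earlier use of glucose-lowering drugs. Section 9.3.3 says that those medications are identified from ATC code together with drug name.

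**The concern.** The research question in section 8 asks for the prescription pattern of each class as well as each compound. A class table answers it only if patients who take a drug of that class are in the class. Under the list as it stands, a patient whose only metformin comes in the metformin/pioglitazone pill is not in the biguanide group, and a patient whose only pioglitazone comes with alogliptin is not in the thiazolidinedione group.

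Index dates are also at stake. A patient who starts on metformin/pioglitazone and later takes metformin alone can have no biguanide index date before the change, so age, comorbidities and renal stage at biguanide start would describe a later moment than first metformin exposure.

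The classes concerned matter to the protocol's own rationale. Section 7 states that "biguanide is contraindicated in moderate or severe RI" and also describes renal restrictions for pioglitazone in Japan. Biguanides and thiazolidinediones are two of the four classes with an omission.

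**Working it through.** There is no stated figure to reproduce. The study is descriptive, with no power calculation, and its size is a database count. The check maps each combination to the classes of its two components and compares that with where section 9.3.1 lists it.

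| Combination | Listed under | Component class not credited |
|---|---|---|
| Alogliptin/pioglitazone | DPP-4 inhibitors | Thiazolidinedione |
| Glimepiride/pioglitazone | Thiazolidinediones | Sulfonylurea |
| Metformin/pioglitazone | Thiazolidinediones | Biguanide |
| Mitiglinide/voglibose | Glinides | Alpha-glucosidase inhibitor |

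**Memberships.** 4 combinations × 2 components = 8 component-class memberships. The list gives 4, so 8 − 4 = 4 are absent, one in each of four classes. DPP-4 inhibitors and glinides lose no one among the listed products. The overall OAD group loses no one either, because every combination is itself a study drug. The estimates of 9,890 OAD and 7,579 DPP-4 inhibitor patients in section 9.5 are therefore not changed by this point.

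**Principle.** Two products are classed by the first-named component (alogliptin, mitiglinide) and two by the second-named (both pioglitazone). Pioglitazone decides the class in two of its three combinations and not in the third. The thiazolidinedione group thus includes some users of fixed-dose pioglitazone and omits others.

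**Class index date.** Section 9.2 says "index date is defined as the date of first prescription for study drug of class". A combination not listed in a class cannot set that class's index date.

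**Washout.** Take a patient who changes from metformin/pioglitazone to metformin within six months. Section 9.2 can be read in two ways:

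- If the washout looks for the same drug or class, the combination is not seen as a biguanide and the patient enters as a new biguanide start.
- If any study drug counts, the combination is itself a study drug and the patient is excluded, so there is no false new start.

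**Flags.** Section 9.3.3 identifies these drugs by ATC code and name, not by the section 9.3.1 list. The rows in section 9.7.1 also cover GLP-1 receptor agonists, SGLT2 inhibitors and insulin, none of which is in that list, so a wider mapping must exist. Whether it splits a combination into its components is not stated.

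**Size.** Let N be the true number of users of a class and s the share who take it only in a combination listed elsewhere. The listed count is N × (1 − s). The documents give no value for s. For assumed values and N = 1,000:

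- s = 1%: 1,000 × 0.99 = 990
- s = 5%: 1,000 × 0.95 = 950
- s = 10%: 1,000 × 0.90 = 900
- s = 20%: 1,000 × 0.80 = 800

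The share s is not the share of users who ever take a combination. One prescription of the class is enough for section 9.7.1, so a patient who also qualifies on the separate drug is still counted. The share who ever take a combination is therefore only an upper limit for s.

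**The case against.** The strongest reply is that putting each combination in one class is explicit and reproducible, in a study that tests no hypothesis. Crediting both classes would place one prescription in two compared groups with the same index date. Compound-level results are unaffected, since each combination is its own entry and the secondary outcome in section 9.3.2.2 concerns drug and dosage. Parts of the objectives and analysis text are blacked out and Figure 1 is not shown, so a rule may exist there.

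Much of this stands. Compound-level tables are sound, and the redacted parts cannot be checked. But a single-class listing is defensible as a convention only if it follows a rule, and none is stated or can be inferred. The overlap argument carries little weight, because a patient on two separate tablets already belongs to two class groups.

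A reader might go further and infer that the washout and the yes/no rows also miss these patients. The documents do not support that. The washout miss arises on only one reading of section 9.2. The per-drug wording, and the fact that an any-drug washout would leave little recent OAD use for the premedication rows to describe, make that reading plausible but do not prove it. A name search for the flags could find both components. Nor do the documents support saying that renal-impairment exposure is lost throughout: any loss shown is at class level.

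**Conclusion.** The point holds for class-level membership and class-level index dates. Followed as written, section 9.3.1 leaves out biguanide, sulfonylurea, thiazolidinedione and alpha-glucosidase inhibitor exposure that comes only in a combination listed under another class. For washout and flags the finding is narrower: the handling of combinations is not settled, and a miss is not shown.

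The size in patients cannot be given; the percentages above are assumptions used for illustration. The conclusion rests on the visible text and would change if a redacted part holds a rule for combinations. It should be corrected before the class tables are programmed, because two programmers could produce different class tables from the present text. It does not threaten the compound-level results.

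**What to change.** Add a mapping table to section 9.3.1 that assigns each of the four combinations to both of its component classes for class-level analyses. Apply it to group membership and the class index date, and state in sections 9.2 and 9.3.3 that the same mapping governs the washout and the concomitant and premedication flags. In the same edit, say whether the washout looks for the same drug, the same class or any study drug. Keep each combination as its own row in the compound-level tables.

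The cost is one table and a few lines of protocol text; no new data are needed and no test is affected. The downside is slightly more overlap between class groups, which already overlap. If the sponsor prefers a single class per combination, the rule should at least be stated and applied consistently, with combination users tabulated separately so that readers can see how many each class omits.
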